For the initial diagnosis and efficacy assessment at 14-21 days posttreatment, two stool samples will be collected from each participant on two consecutive days. All stool samples will be examined for presence of T. trichiura, A. lumbricoides, and hookworm eggs with duplicate Kato-Katz thick smears assessed via bright-field microscopy. The medical history of the participants will be assessed with a standardised questionnaire, in addition to a clinical examination carried out by the study physician before treatment. Parents/caregivers will be interviewed before treatment and at three and 24 hours and 14-21 days post-treatment for the occurrence of AEs. Any potential AEs happening between 3 hours and the respective follow-up time points will be monitored by local healthcare workers and medical intervention provided if necessary. Each participant will be asked to provide a finger-prick blood sample for haemoglobin measurement at baseline. At the same time, anthropometric measurements (i.e. height, and weight) will be taken for all participants.

To determine PK parameters of ivermectin ODTs and standard tablets, a subsample of 12 study participants per relevant treatment arm (ivermectin ODT 200 μ g/kg and ivermectin tablet 200 μ g/kg) will be asked to provide a maximum of 5 micro blood samples per participant using finger pricks at defined time points between 1 hour and 24 hours. To determine the acceptability of ivermectin ODTs compared to standard tablets, the palatability of each formulation will be rated by children aged 4-5 years using a 100 mm visual analogue scale (VAS). Additionally, participants will complete a short questionnaire right after treatment administration.

Statistical analyses

An available case analysis (full analysis set according to the intention to treat principles) will be performed, including all participants with primary endpoint data. Additionally, a per-protocol analysis will be conducted. CRs will be calculated as the percentage of egg-positive participants at baseline who become egg-negative after treatment.

Geometric and arithmetic mean egg counts will be calculated for the different treatment arms before and after treatment to assess the corresponding ERRs. Bootstrap resampling with 5,000 replicates will be used to calculate 95% confidence intervals (CIs) for ERRs.

	Using the DoseFinding package of the statistical software environment
	R , E_{max} models will be implemented to predict the dose-response curves

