4.3 Procedures

4.3.1 Diagnosis

At baseline, all participants will be asked to provide two stool samples. From each stool specimen, duplicate Kato-Katz thick smears (41.7 mg each) [24] will be prepared and read under a microscope for eggs of *T. trichiura*, *A. lumbricoides* and hookworm by experienced technicians. Eggs per gram (EPG) will be assessed by adding up the egg counts from the quadruplicate Kato-Katz thick smears and multiplying this number by a factor of six. For quality control of *T. trichiura* and *A. lumbricoides* egg counts, 10% of slides will be re-read by another laboratory technician. Results are considered correct if the following tolerance margin is not exceeded: (i) No difference in presence/absence of *T. trichiura* and *A. lumbricoides* (ii) egg counts are +/-10 eggs for counts ≤100 eggs or +/-20% for counts >100 eggs (for each species separately). In case discrepancies above the tolerance margin are noted in one or more slides, the respective slides are re-read by the local technicians. The new results are discussed, so that in case of discordant results, slides can be re-evaluated to reach consensus. All microscopically analysed quadruplicate Kato-Katz thick smears will be destroyed after passing the quality control. The same diagnostic approach will be applied at 14-21 days after treatment (see section 4.3.8).

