4.4 Measure to minimise bias

Study participants eligible for treatment will be randomly assigned to one of the six treatment arms using a computer-generated stratified randomisation code. The random allocation sequence with a block size of 6 stratified by two levels of age category (24-47 months and 48-71 months) and two levels of baseline *T. trichiura* infection intensity (light: 1-999 EPG, and moderate or heavy: ≥1000 EPG) will be provided by a statistician. Allocation concealment will be warranted using opaque, sealed envelopes containing the randomisation lists. All treatment arms will be single-blinded (*i.e.* study participants will be blinded) using appearance and texture matching placebos. Only the study pharmacist administering the treatment will be aware of treatment allocation; all trial team members assessing the outcomes will remain uninformed. In the case of accidental unblinding or necessary code breaks, the sponsor will be immediately notified (within 24 hours) and data will be analysed as set forth in section 8.3.

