8.2 Justification of number of trial participants

The main aim of this study is to elucidate the nature of the dose-response relationship. A series of simulations was carried out to determine the required sample size. We assumed different sets of true CRs ranging from very optimistic (10%, 45%, 54%, 58% and 60%) to very pessimistic (15%, 30%, 33%, 34% and 35%) for 0, 100, 200, 300 and 400 μ g/kg, respectively. Assuming a loss to follow-up of 10%, we estimated that enrolling 35 participants per arm will be sufficient to predict the dose-response curve with a precision (defined as median distance between prediction and confidence band) of about 10 %-points in the relevant dose range from 100 μ g/kg to 400 μ g/kg. Additionally, 35 individuals will be included for the standard tablet arm. In total, we anticipate to recruit 210 participants.

The suggested sample size of a maximum 5 PK samples from 24 participants (12 per concerned study arm) is sufficiently high to determine the population PK parameters with a sparse sampling scheme.

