8.3 Description of statistical methods

The primary analysis will use the full analysis set (available case population) according to the intention-to-treat principles defined as all randomised participants who provide any follow-up data. Only randomised participants not providing follow-up data as well as participants who were negative at baseline and erroneously randomised will be excluded from the analysis. In addition, a per-protocol analysis will be conducted. Eligibility for analysis sets will be determined before unblinding. CRs will be calculated as the percentage of egg-positive participants at baseline who become egg-negative after treatment.

EPG will be assessed by adding up the egg counts from the quadruplicate Kato-Katz thick smears and multiplying this number by a factor of six. Geometric and arithmetic mean egg counts will be calculated for the different treatment arms before and after treatment to assess the corresponding ERRs (see formula).

$$ERR = 1 - \frac{\frac{1}{n} e^{\sum \log(EPG_{follow-up} + 1)} - 1}{\frac{1}{n} e^{\sum \log(EPG_{baseline} + 1)} - 1}$$

Bootstrap resampling method with 5,000 replicates will be used to calculate 95% confidence intervals (CIs) for ERR point estimates. Using the DoseFinding package of the statistical software environment R, hyperbolic E_{max} models will be implemented to predict the curves of the dose-response in terms of CRs and ERRs.

Previous similar trials have shown that the proportion of participants lost to follow-up is usually far below 10%, therefore, no imputation of missing data will be performed. Infection status and egg counts of participants with incomplete data at follow-up (*i.e.* only one stool sample available at follow-up) will be estimated based on the available data. This means a participant is considered infected if any sample is positive and EPGs will be calculated as mean egg count of the available sample multiplied by 12.

The safety analysis set will include all treated participants. AEs will be evaluated descriptively focusing on the proportion of participants reporting symptoms before and after treatment in each arm.

Previously established nonlinear mixed-effects (NLME) models will be used to compare and determine PK parameters [21]. Concentrations are measured with a validated LC-MS/MS method [32]. Using NLME, the following key PK parameters will be calculated:

- C_{max} maximal plasma concentration
- t_{max} time to reach C_{max}

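### Allocation is stratified by age and baseline intensity, but the primary cure-rate curve uses crude rates: valid, with standard errors nil to about 10% too wide, and a small optional gain from adjusting

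*Combined protocol and SAP*

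**What the plan says.** Section 4.4 allocates children to six arms in blocks of 6, "stratified by two levels of age category (24-47 months and 48-71 months) and two levels of baseline" T. trichiura intensity, cut at 1000 EPG.

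Section 8.3 states that "CRs will be calculated as the percentage of egg-positive participants at baseline who become egg-negative after treatment", and then that "hyperbolic E_{max} models will be implemented to predict the curves of the dose-response in terms of CRs and ERRs". The synopsis (Statistical analyses) likewise says that Emax "models will be implemented to predict the dose-response curves".

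Section 8.2 sizes the trial, with 35 per arm and 10% loss, on "a precision (defined as median distance between prediction and confidence band) of about 10 %-points" between 100 and 400 µg/kg.

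No section names a stratum term, a baseline covariate or an adjusted cure rate for this curve. None says outright that the curve is unadjusted, but that is the plain reading.

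**The concern.** If a stratification factor predicts cure, stratified arms resemble each other more than simply randomised arms would. The usual variance p(1-p)/n does not know this, so the reported error is larger than the true one. In addition, baseline EPG is known for every child before randomisation, and a two-level stratum uses only part of it.

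Bias is not at stake. What is at stake is how wide the reported uncertainty is, which is the quantity the trial is sized on, and whether the choice of model is fixed before the data are unblinded. The documents do not say how strongly age or intensity predicts cure.

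**Working it through.** **1. The plan's own figure.** Both cure-rate sets in section 8.2 lie on hyperbolic Emax curves, CR(d) = E0 + Emax·d/(d + ED50).
- Optimistic: E0 0.10, Emax 0.583, ED50 66.7.
- Pessimistic: E0 0.15, Emax 0.225, ED50 50.

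With 35 × 0.9 = 31.5 evaluable per arm, arm variance p(1-p)/31.5 and 95% confidence (assumed, since the plan gives no level for this band), the delta method gives a median half-width over 100-400 µg/kg of 10.4 points (optimistic) and 9.9 (pessimistic) on a 1 µg/kg grid. On a 10 µg/kg grid it gives 10.6 and 10.0. The crude fit therefore delivers the stated figure of about 10.

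**2. Crude standard error against the stratified design (400 vs 0 µg/kg).** Assumptions: OR between light and heavier infection of 1 to 10, 50-80% of children light, age not prognostic. Worked case: optimistic set, OR 10, 50% light.
- Stratum cure rates that average 10% and 60%: 17.87% / 2.13% at 0 µg/kg and 84.58% / 35.42% at 400 µg/kg.
- Crude formula: √[(0.10×0.90 + 0.60×0.40)/31.5] = √(0.330/31.5) = 0.1024.
- Within-stratum variances: 0.5×(0.1787×0.8213 + 0.0213×0.9787) = 0.0838, and 0.5×(0.8458×0.1542 + 0.3542×0.6458) = 0.1796.
- Stratified formula, with 6 × 31.5 = 189 children overall: √[(0.0838 + 0.1796)/31.5 + 0.25×(0.4916 - 0.1574)²/189] = √(0.00836 + 0.00015) = 0.0922.

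The same two formulas over both cure-rate sets and 50-80% light give:

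| OR, light vs heavier | Crude ÷ stratified SE |
|---|---|
| 1 | 1.000 |
| 2 | 1.006-1.011 |
| 3 | 1.013-1.028 |
| 10 | 1.034-1.110 |

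The stratified formula assumes near-perfect balance. Incomplete blocks and random loss leave a little imbalance. In simulation (blocks of 6, 10% loss) the true SE of the crude difference is 0.0935 at OR 10, so the crude formula is 0.1024/0.0935 = 1.095 times too large. At OR 2-3 it is about 0.0999, and 0.1024/0.0999 = 1.025. Over the range this is 0-2.5% at OR 2-3 and about 3-10% at OR 10. The SE a trial prints uses estimated rates and averages about 2% below the formula (0.1006 against 0.1024 in simulation), so the excess in practice is about two points smaller.

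**3. Real gain from adjusting for the strata.** In the same simulations, the true SE, crude against strata-adjusted, is 0.0999 against 0.0997 at OR 2-3. At OR 10 it is 0.0935 against 0.0922, a gain of 1 - 0.0922/0.0935 = 1.4%. The stratified allocation has already captured the rest.

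**4. Real gain from log baseline EPG.** Simulation with 4,000 runs per scenario; assumed 65% light, SD of ln EPG 1.5, age not prognostic. Root mean squared error of the curve, in points, crude → adjusted:

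| OR per tenfold fewer eggs | Optimistic | Pessimistic | Fall in mean squared error |
|---|---|---|---|
| 1 | 5.62 → 5.62 | 5.06 → 5.06 | about 0% |
| 2 | 5.55 → 5.52 | 5.00 → 4.97 | about 1% |
| 3 | 5.52 → 5.46 | 4.97 → 4.92 | about 2% |
| 10 | 5.34 → 5.17 | 4.82 → 4.64 | 6-7% |

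For example, 1 - (5.17/5.34)² = 6.3%. With SD 1.0-2.0 and 50-80% light, the range at OR 10 is 3.8-11.9%.

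**5. Reported half-width with log EPG.** With the covariance scaled by n/(n-8) for the 8 fitted terms, the optimistic set moves from 10.37 to 10.56 at OR 1 (0.19 wider), 10.37 to 10.43 at OR 2, 10.37 to 10.26 at OR 3 and 10.38 to 9.64 at OR 10. At OR 10 the band narrows by 7% but root mean squared error falls by only 3%, so part of the narrowing corrects a conservative error bar and is not added precision.

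**6. A second simulation under other assumptions.** With 40% of children at or above 1000 EPG and ORs of 1 to 5 per SD of log EPG, the curve's true sampling half-width changes by +1% to -2%. With only 10% at or above 1000 EPG, it falls 3-5% at OR 3 and about 7% at OR 5. At OR 5 and 40%, the crude SE for 400 vs 0 µg/kg averages 0.1009 against a true 0.0936 (optimistic) and 0.1044 against 0.0996 (pessimistic).

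**The case against.** The case for leaving the plan alone is strong. The crude analysis is unbiased and meets its precision target, and the stratified design has already captured nearly all that the strata can offer. If the covariates are weak, adjustment makes the reported band slightly wider. There is also slack already: section 8.3 says that "the proportion of participants lost to follow-up is usually far below 10" per cent, and with no loss the half-width falls from 10.4 to 9.9 points, more than adjustment yields at moderate prognostic strength. The adjusted model is less simple and needs ethics approval.

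The numbers are also soft. The two simulations differ on the crude reported half-width for the pessimistic set (about 9.8 against 8.6 points), so differences of a tenth or two mean little. Coverage of the crude curve was 93.9-95.3% in one and as low as 90% in the other, where adjustment did not improve it. The excess width is therefore shown for the arm difference, not for the fitted band as a whole.

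All of this stands. It limits the point to an optional improvement but does not remove it: the reported error does not reflect the design, and the covariates cost nothing to use.

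A reader might infer two stronger things. One is that stratified allocation makes an unadjusted analysis wrong. It does not: the estimate stays unbiased and its error bars err, if at all, mainly on the cautious side. The other is that adjusting for the strata is worth extra children per arm. That would compare the adjusted variance with p(1-p)/n, which is not the true variance of the crude estimate here; step 3 shows a real gain near nil.

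**Conclusion.** The point holds as a minor, optional improvement, not an error, and the sample size need not change. The crude fit ignores the stratified design in its standard errors, by nothing to about 10% for 400 versus 0 µg/kg. Log baseline EPG brings a further real gain that is negligible to small unless intensity is strongly prognostic. The size rests on assumed prognostic strength, share of light infections and EPG spread, none of which the documents give. The direction does not depend on those assumptions: stratifying on a factor that predicts cure cannot make the crude variance formula too small beyond the usual small-sample error.

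**What to change.** In section 8.3, before unblinding:
1. Fit a logistic model of cure on randomised arm (all six), age stratum and log baseline EPG. Standardise to the pooled trial population to obtain marginal cure rates per arm with their covariance matrix, including covariate sampling and a small-sample scaling such as n/(n-8). Standardising keeps the question the same; a conditional odds-ratio curve would answer another one.
2. Fit the Emax curve to the 0-400 µg/kg ODT-series estimates (placebo as 0) and that covariance, leaving the standard-tablet arm out of the curve.
3. Keep the crude fit as a sensitivity analysis.
4. State what happens if an arm has no cures. At a true rate of 10% this has probability 0.90^31.5 = 3.6%, and it affects the crude variance too. A Firth-type penalty used only in that case is one option.

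Log EPG is always defined. Section 8.3 says that "participants who were negative at baseline and erroneously randomised will be excluded from the analysis", and EPG comes from "adding up the egg counts from the quadruplicate Kato-Katz thick smears and multiplying this number by a factor of six", so the minimum is 1 × 6 = 6, or 2 × 6 = 12 with the two positive slides required by section 5.2.

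Cost: no new data. Section 9.1 requires a written, signed amendment and ethics committee approval. The model is slightly more complex, and the reported band may be up to about 0.2 points wider if the covariates are weakly prognostic. If the sponsor prefers the crude fit, one sentence stating that the primary curve is unadjusted would settle the matter.

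### Section 8.3 fits only a hyperbolic Emax curve, although the shape of the dose-response is what the trial sets out to learn; a shape sensitivity curve and per-arm intervals should be added

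*Combined protocol and SAP*

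**What the plan says.** Section 8.2 of the combined protocol and SAP states the purpose: "The main aim of this study is to elucidate the nature of the dose-response relationship". Section 8.3 then names one model family for both cure rates and egg reduction rates: "hyperbolic E_{max} models will be implemented to predict the curves of the dose-response in terms of CRs and ERRs". The synopsis also names only Emax: "E_{max} models will be implemented to predict the dose-response curves".

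E0, Emax and ED50 are estimated from the data, so the plan fixes the family and not the whole curve. Hyperbolic means Hill slope 1, so the curve cannot turn down and has no inflection. Neither section mentions a candidate set, a sigmoid alternative, a goodness-of-fit check or a sensitivity analysis of shape. Section 8.3 calculates CRs as percentages, which do not depend on any curve, but specifies no interval for them. Its 95% bootstrap intervals are for the egg reduction rates.

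Section 8.2 bases the sample size on simulations over several sets of true CRs, of which it prints the two extremes: "very optimistic (10%, 45%, 54%, 58% and 60%) to very pessimistic (15%, 30%, 33%, 34% and 35" per cent, at 0, 100, 200, 300 and 400 µg/kg. It concludes that "enrolling 35 participants per arm will be sufficient to predict the dose-response curve" to within about 10 percentage points over 100-400 µg/kg, allowing for 10% loss to follow-up.

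**The concern.** The shape is the stated unknown, but the only planned fit assumes it. If cure rises slowly at low doses and then climbs, or falls off at the top dose, a hyperbolic Emax fit smooths that away. Its confidence band reflects sampling error given the assumed shape and carries no allowance for the shape being wrong.

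The fitted curve is the primary result, and section 3 says the trial should identify the most appropriate dose and prepare for phase 3. A misplaced curve at 100 µg/kg or at 400 µg/kg would bear directly on that reading. The precision in 8.2 gives no protection if it was worked out only for truths of the fitted shape.

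**Working it through.** **Inputs from the documents.** Five doses on the curve (0, 100, 200, 300 and 400 µg/kg); 35 enrolled per arm; 10% loss, so 35 × 0.9 = 31.5, taken as 31 or 32 evaluable; the two printed CR sets; stated precision about 10 points.

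**Assumptions, because the documents are silent.** Pointwise 95% bands; ED50 searched over 0.4-600 µg/kg; least squares on the probability scale or weighted least squares on the logit scale; delta-method or bootstrap bands; the alternative shapes below.

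**Step 1. Do the printed CR sets lie on a hyperbolic Emax?** The model is CR(d) = E0 + Emax × d / (ED50 + d).

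- Optimistic set, E0 = 10, matched at 100 and 400 µg/kg: 35(ED50 + 100)/100 = 50(ED50 + 400)/400. So 0.225 × ED50 = 15, ED50 = 66.7 and Emax = 35 × 166.7/100 = 58.3. Predictions are 53.75 at 200 (printed 54) and 57.7 at 300 (printed 58).
- Pessimistic set, E0 = 15: 15(ED50 + 100)/100 = 20(ED50 + 400)/400. So 0.10 × ED50 = 5, ED50 = 50 and Emax = 15 × 150/100 = 22.5. Predictions are 33.0 at 200 (printed 33) and 34.3 at 300 (printed 34).

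A least-squares fit to all five points misses by at most 0.16 and 0.19 points. Both sets are hyperbolic Emax curves up to rounding.

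**Step 2. Reproduce the stated precision.** Binomial counts were simulated from these sets (4,000 trials, 31-32 per arm) and the Emax model was fitted with delta-method bands. The median half-width over 100-400 µg/kg is 9.8-10.5 points (optimistic) and 9.5-10.3 points (pessimistic), with mean coverage of 94-97%. The stated figure of about 10 points reproduces.

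**Step 3. Keep the Emax analysis and change the true shape (32 per arm).** The ranges cover separate runs with different fitting scales and band types.

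| True CR (%) at 0/100/200/300/400 | Bias of the Emax fit (points) | Coverage of the 95% band |
|---|---|---|
| Printed planning sets | at most 1.3 | 93-96% (bootstrap) |
| Sigmoids, Hill 3-4: 10 / 13-22 / 37-47 / 53-57 / 60 | about +7 to +10 at 100 | at 100: about 5% to 88%, see below |
| Hump: 10/45/54/50/45 | -5.5 to -5.9 at 200; +5.4 to +5.8 at 400 | 68-80% at 200; 77-80% at 400 |
| Milder sigmoid inside the planning range: 10/30/50/58/60 | up to about 3-4 | about 86-93% (bootstrap) |
| Linear, 10 to 60 | up to 4 | about 82-95% (bootstrap); 92-99% (delta method) |

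The bias for the sigmoids is stable, but the coverage is not. For the steepest (ED50 200, Hill 4), coverage at 100 µg/kg ran from about 5% to 56% according to fitting scale and band type. The 88% is the mildest (ED50 150, Hill 3) with delta-method bands; a bootstrap band gave 52% for the same truth.

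**Step 4. Does the band signal the problem?** No. Across these shapes the median half-width stays at 9.4-11.7 points (delta method). With bootstrap bands it is 7.9-8.9 points under the non-Emax truths run, against 9.5 and 8.5 under the two planning sets.

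**Step 5. How much do the per-arm CRs show?** The half-width is 1.96 × √[p(1 - p)/32]. At p = 0.30 it is 15.9 points; at p = 0.54 it is 17.3 points. A displacement of 7-10 points is hard to see against that. A 5% lack-of-fit test detected the sigmoids in only 20-48% of runs.

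**Step 6. What does averaging gain?** Hyperbolic Emax, sigmoid Emax, linear and quadratic fits were weighted in proportion to exp(-AIC/2), with the weighting repeated inside the bootstrap. Coverage was 90-96% over 100-400 µg/kg in the truths run. When Emax is true, the half-width grows by 0.4-2.8 points (for example 9.4 to 11.7 at 200 µg/kg). A similar set that also included an exponential model cost about 1.5 points (9.5 to 11.0 and 8.5 to 10.0). Its weakest result was under a sharper hump (10/45/60/50/40), with mean coverage of 90.8% and 86.2% at 300 µg/kg. Averaging helps greatly but is not a guarantee.

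**The case against.** The strongest reply is that hyperbolic Emax is a reasonable working model for a small phase 2 estimation trial, and that the large errors come from shapes chosen to break it. The three sigmoids put the CR at 100 µg/kg at 13-22%, below the 30% of the plan's own pessimistic set, and no section suggests a threshold or a downturn. This largely stands. The size of the harm is conditional, and the smooth sigmoid inside the planning range is the fairer mild case. Sharper shapes inside that range do worse, however: 10/30/54/58/60 gave 68% coverage at 200 µg/kg, and 10/30/33/34/60 gave 44% at 300 µg/kg.

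A reader might infer three stronger things that the documents do not support.

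- *That the precision was tested only where Emax is true.* Section 8.2 refers to a series of simulations and prints only the end sets. The sets in between are not shown, so the claim must stop at what is shown.
- *That nothing in the plan could reveal a wrong shape.* Per-arm CRs are calculated, and egg reduction rates are given with bootstrap intervals. Neither needs a curve. What is missing is an interval for the CRs and a planned comparison with the fit.
- *That the band is simply too narrow.* The failure is mainly one of position: the width barely changes and the centre moves.

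It is also fair that four sigmoid parameters on five doses are weakly identified. That is a reason to use the sigmoid inside an average and as a sensitivity analysis, and not as the primary model.

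**Conclusion.** The point holds as a limited one that should be acted on. The plan aims to learn the shape, fits one shape, and has no planned way to show how far the answer depends on that choice. The 10-point precision in 8.2 is not an arithmetic error. It reproduces, on the condition that hyperbolic Emax is true.

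The size depends on the truth: a serious misplacement at 100 µg/kg for steep sigmoids, clear under-coverage at 200 and 400 µg/kg for a hump, and a modest loss for a mild sigmoid or a straight line. No single coverage figure for the sigmoids should be quoted as established, because the plan gives neither the fitting scale nor the type or level of the curve band. Only cure rates were examined; the documents give no egg-count distribution from which to simulate the egg reduction rate curve. None of this shows that the true curve departs from Emax or that the primary fit should be replaced.

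**What to change.** Keep the hyperbolic Emax model as the primary fit and make three additions before unblinding.

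1. In 8.3, report the observed CR in each arm with a 95% CI and plot these on the fitted curve.
2. In 8.3, pre-specify a sensitivity curve for the CR that averages hyperbolic Emax, sigmoid Emax, linear and quadratic models by AIC weight, with bootstrap bands that repeat the weighting in each resample. Report it beside the primary curve. It need not be a condition for drawing conclusions from the primary fit: a rule that the two bands must agree would need a definition of agreement and would act as a veto.
3. In 8.2, state that the precision of about 10 points assumes a hyperbolic Emax shape.

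While editing 8.3, name the fitting scale and the type and level of the curve band, since coverage depends on them.

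The cost is SAP wording and a little more programming. The downside is a sensitivity band about 0.4-3 points wider than the primary band when Emax is true. Design, sample size and primary fit do not change. Fixing the candidate models in advance matters, because shapes chosen after seeing the data would carry little weight.

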4.3.8 Efficacy assessment

The efficacy of the treatment will be determined at 14-21 days post-treatment by collecting another two stool samples, which will be microscopically examined for *T. trichiura*, *A. lumbricoides* and hookworm eggs using quadruplicate Kato-Katz thick smears (two slides per sample). Quality control will be performed as described for the initial diagnosis (see section 4.3.1). All microscopically analysed quadruplicate Kato-Katz thick smears will be destroyed after passing the quality control.

Participants will be considered cured for an infection if no corresponding eggs are found in the followup stool samples. At the end of the study, all participants remaining positive for *T. trichiura* or any coinfection will be treated with the currently best recommended treatment.

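### As worded, the section 8.3 rule for children with one follow-up stool sample halves their EPG and biases the egg reduction rates upward

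*Combined protocol and SAP*

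**What the plan says.** Section 4.3.1 sets the slide mass and the number of slides per specimen: "From each stool specimen, duplicate Kato-Katz thick smears (41.7 mg each"). Section 4.3.8 repeats the slide count for follow-up: "quadruplicate Kato-Katz thick smears (two slides per sample").

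With complete data, section 8.3 states: "EPG will be assessed by adding up the egg counts from the quadruplicate Kato-Katz thick smears and multiplying this number by a factor of six". Section 4.3.1 has the same rule.

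For incomplete follow-up data, explained as "only one stool sample available at follow-up", section 8.3 gives two rules. For infection status, "a participant is considered infected if any sample is positive". For intensity, "EPGs will be calculated as mean egg count of the available sample multiplied by 12".

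Under section 8.3, EPG feeds the geometric and arithmetic mean ERRs, their bootstrap confidence intervals and the Emax curves for ERR. No section defines the mean egg count of a sample as its two-slide total, and none explains the 12.

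**The concern.** The multiplier belongs to a sum but is attached to a mean. If the sentence is programmed literally, children with one follow-up sample are on half the scale of children with two. Their own baseline EPG is on the full scale, because the one-sample rule is written for follow-up only and eligibility (section 5.2) is assessed on four baseline slides.

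The error therefore goes one way: follow-up intensity is understated and the ERR is overstated. The rule is not limited to one species, so it also reaches the *A. lumbricoides* and hookworm ERRs. The bootstrap intervals would not reveal it, because every resample carries the same halved values. If the share of one-sample children differs between arms, comparisons between doses are distorted as well.

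**Working it through.** **Inputs.** Slide mass 41.7 mg and two slides per sample (sections 4.3.1 and 4.3.8); sum of four slides × 6 for complete data (sections 4.3.1 and 8.3); mean × 12 for one follow-up sample (section 8.3).

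**Formula.** EPG = eggs counted × 1000 / (number of slides × 41.7 mg).

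**The plan's own factor.** Sum of four slides: 1000 / (4 × 41.7) = 1000 / 166.8 = 5.995, so × 6 is reproduced. Since the sum is four times the mean, this equals mean per slide × 24.

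**One sample, two slides.**
- Sum of two slides: 1000 / 83.4 = 11.99, so × 12.
- Mean of two slides: 1000 / 41.7 = 23.98, so × 24.

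**Example, 10 eggs on every slide.**

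| Rule | Calculation | EPG |
|---|---|---|
| Complete data | 40 × 6 | 240 |
| One sample, as written | 10 × 12 | 120 |
| One sample, sum × 12 | 20 × 12 | 240 |
| One sample, mean × 24 | 10 × 24 | 240 |

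**Effect on the arithmetic mean ERR.** Let f be the share of an arm with one follow-up sample, and assume these children have the same average intensity as the rest. The follow-up mean is multiplied by (1 − f/2), so

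reported ERR = 1 − (1 − true ERR) × (1 − f/2).

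The plan does not give f, so a range is assumed. The 10% in section 8.2 is loss to follow-up, which is a different quantity.

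| True ERR | f = 2% | f = 5% | f = 10% | f = 20% |
|---|---|---|---|---|
| 50% | 50.5% | 51.25% | 52.5% | 55.0% |
| 80% | 80.2% | 80.5% | 81.0% | 82.0% |
| 95% | 95.05% | 95.1% | 95.25% | 95.5% |

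**Effect on the geometric mean ERR.** Halving a share f of the values lowers the geometric follow-up mean by at most 1 − 2^(−f): 3.4% at f = 5% and 6.7% at f = 10%. This ceiling needs every affected child to be egg-positive. These are changes in the follow-up mean, not ERR points. As an illustration, assume a baseline geometric mean of 500 EPG, 200 EPG in each child still positive, f = 10%, and a geometric mean formed in the usual way on log(EPG + 1):

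| Still positive | True ERR | Reported ERR |
|---|---|---|
| 90% | 76.6% | 78.0% |
| 65% | 93.9% | 94.2% |
| 40% | 98.5% | 98.6% |

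**Effect between arms.** With equal f, the inflation (1 − ERR) × f/2 is largest in the least effective arm. At f = 10%, arms with true ERRs of 50% and 80% are reported as 52.5% and 81.0%, so a difference of 30 points becomes 28.5. With unequal f, a difference can appear where there is none: two arms with a true ERR of 50%, one with f = 0 and the other with f = 10%, are reported as 50% and 52.5%.

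**The case against.** The best defence is that the sentence names the stool sample, not the slide. A sample is two slides, 83.4 mg, and 12 is the correct factor for a sample's total count. If S1 and S2 are the totals of two samples, their mean times 12 is (S1 + S2) × 6, which is the complete-data rule; with one sample it becomes S1 × 12. On this reading nothing is halved, and the only slip is the word mean. This is probably how the sentence arose. It is not the plain reading, though: with a single sample there is nothing to average except its two slides, and section 8.3 speaks of adding up counts when it means a sum. A programmer following the text would halve the EPG.

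The objections on scope stand:
- The primary endpoint does not use the factor. Cure rates, the cure-rate dose-response curve and the sample-size simulations are untouched.
- Only children with exactly one follow-up sample and at least one egg counted are affected, since a zero count stays zero. In an arm of 35, 10% would be 3.5 children.
- The shift shrinks as efficacy rises, and with equal shares it slightly compresses dose differences rather than exaggerating them.

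**Conclusion.** The rule is wrong as worded. It gives exactly half the EPG that the plan's own complete-data rule implies, and the resulting bias in ERR is upward. That part rests only on figures in the document.

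The arm-level size rests on an assumed share of one-sample children with average intensity. For shares of 2% to 10%, the inflation of the arithmetic ERR runs from 0.5 to 2.5 points at a true 50%, and from 0.2 to 1.0 points at a true 80%. The importance is modest, because only secondary intensity results, ERRs and the ERR curves are exposed. It is nevertheless a fixed conversion error in a pre-specified derivation, and no later analysis step would remove it.

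**What to change.** Replace the one-sample sentence in section 8.3 with: EPG is the sum of the egg counts on the two available slides multiplied by 12 (equivalently, the mean per slide multiplied by 24). A single rule for everyone would be better still: mean egg count per available slide multiplied by 24. It agrees with the existing factor of 6 for four slides and also covers a single missing slide. If the two-slide total was meant all along, the wording still needs this correction.

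The change is one sentence, needs no new data or procedures, and should be documented as section 9.1 requires before the ERR analysis is programmed. Reporting the number of one-sample children per arm would show how many values the rule touches.
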